11.2 Analysis of Adverse Events

11.2.1 Treatment-Emergent Adverse Events

Treatment-emergent adverse events (TEAEs) are defined as any event with an onset that is after the first dose of study drug and with an onset date within 105 days after the last dose of study drug in the analysis period, or prior to the first dose in the subsequent period for subjects who entered in to the subsequent period. Events where the onset date is the same as the study drug start date are assumed to be treatment-emergent, unless the adverse event start time is prior to the study drug start time. If an incomplete onset date is collected for an adverse event, the event will be assumed to be treatment-emergent unless there is other evidence that confirms that the event is not treatment-emergent (e.g., the event end date is prior to the study drug start date).

The data cutoff date (December 15, 2017) will be applied to TEAEs during the interim analysis, in accordance to the duration of study drug exposure defined up to this cutoff date.

Summary tables will be presented as follows:

1. Adverse Event Overview

The number and percentage of subjects experiencing treatment-emergent adverse events will be summarized for the following adverse event categories.

- Any AE
- Any AE that was assessed as related to study drug by the investigator
- Any severe AE
- Any serious AE (SAE)

- Any SAE that was assessed as related to study drug by the investigator
- Any AE leading to discontinuation of study drug.
- Any AE leading to death.
- Any deaths
- Areas of Safety Interest

2. Adverse Events by System Organ Class and Preferred Term

TEAEs will be summarized and presented using primary Medical Dictionary for Regulatory Activities (MedDRA) system organ classes (SOCs) and preferred terms (PTs). The SOCs will be presented in alphabetical order, and the PTs will be presented in alphabetical order within each SOC.

Subjects reporting more than one adverse event for a given MedDRA preferred term will be counted only once for that term (most severe incident for the severity tables and most related incident for the relationship tables). Subjects reporting more than one type of adverse event within a SOC will be counted only once for that SOC. Subjects reporting more than one type of adverse event will be counted only once in the overall total.

In addition, the number and percentage of adverse events with causal relationship between the events and the study drug will be summarized using the same conventions described above.

3. Adverse Events by Maximum Severity

The severity grading of AEs follows Rheumatology Common Toxicity Criteria (RCTC).

- Grade 1 – mild
- Grade 2 – moderate
- Grade 3 – severe
- Grade 4 – life threatening

Adverse events will be summarized by maximum severity. If a subject has an adverse event with unknown severity, then the subject will be counted in the

severity category of "unknown," even if the subject has another occurrence of the same event with a severity present. The only exception is if the subject has another occurrence of the same adverse event with the most extreme severity (life threatening). In this case, the subject will be counted under the "life threatening" category.

4. Adverse Events by Maximum Relationship

Adverse events will be summarized by maximum relationship to study drug, as assessed by the investigator. Relationship of an AE to study drug is assessed by the investigator and collected in the CRF as 'Yes' or 'No.' If a subject has an adverse event with unknown relationship, the subject will be counted in the relationship category of "unknown," even if the subject has another occurrence of the same event with a relationship of "No." If the subject has another occurrence of the same adverse event with a relationship assessment of "Yes," the subject will be counted under the "yes" category.

A listing of all pretreatment (i.e., events start prior to the first study drug injection) serious adverse events will be provided.

The following tables are planned.

Treatment-emergent adverse events will be summarized as follows:

- Grouped by SOC and PT
- Grouped by SOC, PT and maximum relationship to study drug
- Grouped by SOC, PT and maximum severity

Treatment-emergent SAEs will be summarized as follows:

- Grouped by SOC and PT
- A by-subject listing will be provided

Pre-treatment SAEs will be summarized as follows:

- A by-subject listing will be provided

Treatment-emergent adverse events leading to death or premature discontinuation of study drug will be summarized as follows:

- Grouped by SOC and PT
- Separate listings by subject for deaths and premature terminations of study drug due to adverse events will be provided.

Treatment-emergent areas of safety interest will be summarized as follows:

- Grouped by SOC and PT
- A listing by subject will be provided.

Areas of Safety Interest

Areas of Safety Interest groupings are listed in [Table 10](#). These events are of interest due to a higher rate in the moderate to severe psoriasis population, or of interest for all immunoglobulin products or products in general.

The final list will be based on the most updated final version of risankizumab Product Safety Statistical Analysis Plan, which is consistent to the most updated risankizumab Risk Management Plan.

Table 10. Areas of Safety Interest

ASI Grouping	Categories (ASI)	Search Criteria	Terms to Display	Include in AE Overview (Y/N)
Adjudicated CV Events	MACE	Adjudicated events	
Display underlined terms defined by the following adjudicated terms:
 
 • CV Death which includes CETERM values: Fatal CV, Fatal PE, Fatal Non-Cardiac/Non-Neuro Arterial Thrombosis/Thromboembolism, Undetermined Death, Not assessable death (cardiac/neuro/thrombotic), Fatal Stroke • Myocardial infarction • Stroke 	Y
	Extended MACE	Adjudicated events	
Display underlined terms from MACE and underlined terms below:
 
 • Hospitalization for Unstable Angina • Coronary Revascularization Procedures 	N

Table 10. Areas of Safety Interest (Continued)

ASI Grouping	Categories (ASI)	Search Criteria	Terms to Display	Include in AE Overview (Y/N)
Adjudicated CV Events (continued)	Other CV events	Adjudicated events	
Display underlined terms defined by the following adjudicated terms:
 
 • Thrombotic events which includes CETERM values: Deep Vein Thrombosis, TIA, Pulmonary Embolism, Non-fatal Non-Cardiac/Non-Neurological Arterial Thrombosis/ Thromboembolism, Other Venous Thrombosis, specified (non-fatal) • Cardiac arrhythmia which includes CETERM of: Clinically Significant Arrhythmia • Congestive heart failure which includes CETERM of Heart Failure • Hypertensive emergency 	N
Serious infections, TB, fungal and opportunistic infections (including herpes zoster)	Serious infections	Serious PTs of the CMQ (company MedDRA query) Infections (CMQ 80000018)	PTs	Y
	TB	Tuberculosis (including Investigations) CMQ (code 80000033)	PTs	Y
	Opportunistic infections	Opportunistic infections CMQ (code 80000073)	PTs	N

Table 10. Areas of Safety Interest (Continued)

ASI Grouping	Categories (ASI)	Search Criteria	Terms to Display	Include in AE Overview (Y/N)
Serious infections, TB, fungal and opportunistic infections (including herpes zoster) (continued)	Fungal infections	Fungal infections CMQ (code 80000063)	PTs	N
	Herpes Zoster	Herpes zoster CMQ (code 80000175)	PTs	N
Malignancies	All possible malignancies	Narrow – Malignancies (SMQ 20000090)	PTs	N
	Malignant Tumours	Narrow – Malignant tumours (SMQ 20000194)	PTs	Y
	Non-melanoma skin cancer (NMSC)	Broad – Skin malignant tumours (SMQ 20000204) excluding terms identified by the Melanoma CMQ (code 80000119)	PTs	N
	Malignant Tumours excluding NMSC	'Malignant Tumours excluding NMSC' is identified by the 'Malignant Tumours' search excluding terms identified by the 'Non-melanoma skin cancer (NMSC)' search.	PTs	Y

Table 10. Areas of Safety Interest (Continued)

ASI Grouping	Categories (ASI)	Search Criteria	Terms to Display	Include in AE Overview (Y/N)
Hypersensitivity Reaction	Hypersensitivity	Narrow – Hypersensitivity (SMQ 20000214)	PTs	Y – serious events only
	Anaphylactic Reaction	Narrow – Anaphylactic reaction (SMQ 20000021)	PTs	N
Hepatic Events	Hepatic Events	Broad – Hepatic failure, fibrosis and cirrhosis and other liver damage-related conditions (SMQ 20000013) Broad – Hepatitis, non-infectious (SMQ 20000010) Broad – Cholestasis and jaundice of hepatic origin (SMQ 20000009) Broad – Liver related investigations, signs and symptoms (SMQ 20000008) Narrow – Liver-related coagulation and bleeding disturbances (SMQ 20000015)	PTs	N

Adverse Event per 100 Patient-Years of Exposure

AEs occurring during the entire study will be presented by event rate per 100 patient years. These will be presented for any TEAEs, serious adverse events, Areas of Safety Interest.

AEs per 100 patient-years of exposure is defined as the number of AEs divided by the total exposure in 100 patient-years. Note that one event per preferred term per day per subject will be counted in the calculation of the number of AEs (i.e., a preferred term will not be counted twice on the same day for the same subject). See the calculation method below.

$$100 \times \frac{\text{Number of TEAEs}}{\text{Total Patient Years}}$$

where total patient years is defined as the sum of the study drug exposure (defined as date of last dose – date of first dose + 105 days (5 half-lives)) of all subjects normalized by 365.25, and rounded to one decimal place.

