5.3.6.2 Adverse event collection and reporting

AE Collection

[figure not shown]
The Investigator shall maintain and keep detailed records of all AEs in their patient files. The following must be collected and documented on the appropriate CRF by the investigator:

- From signing the informed consent onwards through the residual effect period (REP) until individual patient's end of trial:
 - all AEs (serious and non-serious) and all AESIs.

However, if an individual patient discontinues trial medication prematurely but stays in the trial (i.e., if further visits including telephone visits, or vital status assessments are planned) from then on and until the individual patient's end of the trial the investigator must report related SAEs and related AESIs

- After the individual patient's end of trial:

The investigator does not need to actively monitor the patient for AEs but should only report relevant SAEs and relevant AESIs of which the investigator may become aware of.

The REP is defined as 15 weeks after the last trial medication application. All AEs which occurred through the treatment phase and throughout the REP will be considered as on treatment please see [Section 7.3.4](#). Events which occurred after the REP will be considered as post treatment events.

AE reporting to sponsor and timelines

The investigator must report SAEs, AESIs, and non-serious AEs which are relevant for the reported SAE or AESI, on the BI SAE form via fax immediately (within 24 hours) to the sponsor's unique entry point (country specific contact details will be provided in the ISF). The same timeline applies if follow-up information becomes available. In specific occasions the investigator could inform the sponsor upfront via telephone. This does not replace the requirement to complete and fax the BI SAE form.

All SAEs and AESIs must be reported immediately to the head of the trial site.

With receipt of any further information to these events, a follow-up SAE form has to be provided. For follow-up information the same rules and timeline apply as for initial information.

Information required

For each AE, the Investigator should provide the information requested on the appropriate CRF pages and the BI SAE form. The Investigator should determine the causal relationship to the trial medication.

The following should also be recorded as an (S)AE in the eCRF and SAE form (if applicable):

- Worsening of the underlying disease or of other pre-existing conditions

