7.3.4 Safety analyses

AEs will be coded using the Medical Dictionary for Regulatory Activities (MedDRA) coding dictionary. Standard AbbVie summary tables and listings will be produced. All AEs with an onset between start of treatment and end of the REP, a period of 15 weeks after the last dose of trial medication, will be assigned to the treatment period for evaluation.

All treated patients will be included in the safety analysis. In general, safety analyses will be descriptive in nature and will be based on AbbVie standards. No hypothesis testing is planned.

Statistical analysis and reporting of AEs will concentrate on treatment-emergent AEs. To this end, all AEs occurring between start of treatment and end of the REP will be considered 'treatment-emergent'. The residual effect period is defined as 15 weeks after the last trial medication application. Adverse events that start before first drug intake and deteriorate under treatment will also be considered as 'treatment-emergent'.

Frequency, severity, and causal relationship of AEs will be tabulated by system organ class and preferred term after coding according to the current version of the MedDRA.

Laboratory data will be analysed both quantitatively as well as qualitatively. The latter will be done via comparison of laboratory data to their reference ranges. Values outside the reference range as well as values defined as clinically relevant will be highlighted in the listings. Treatment groups will be compared descriptively with regard to distribution parameters as well as with regard to frequency and percentage of patients with abnormal values or clinically relevant abnormal values.

Vital signs, physical examinations, or other safety-relevant data observed at screening, baseline, during the course of the trial and at the end-of-trial evaluation will be assessed with regard to possible changes compared to findings before start of treatment.

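### SAP 11.2.1 defines treatment-emergent AEs by post-dose onset only and, without explanation, omits the protocol's rule for AEs that start before first drug intake and worsen on treatment

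*SAP*

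**What the plan says.** Protocol 7.3.4 gives two routes to treatment-emergent status.

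- By timing: "all AEs occurring between start of treatment and end of the REP will be considered 'treatment-emergent", where "The residual effect period is defined as 15 weeks after the last trial medication application".
- By worsening: "Adverse events that start before first drug intake and deteriorate under treatment will also be considered" as treatment-emergent.

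SAP 11.2.1 keeps the first route only: "Treatment-emergent adverse events (TEAEs) are defined as any event with an onset that is after the first dose of study drug". It closes the window 105 days after a period's last dose, or when dosing in the next period begins. It adds a rule for incomplete dates and one for same-day onset, under which an event on the dosing day counts "unless the adverse event start time is prior to the study drug start time". Neither rule deals with worsening.

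For events that start before the first injection, SAP 11.2.1 plans a by-subject listing, restricted to serious events. SAP 11.2.2 lists deaths and all SAEs.

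On data capture, Protocol 5.3.6.2 collects AEs from consent onwards and asks sites to record as an (S)AE: "Worsening of the underlying disease or of other pre-existing conditions".

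**The concern.** SAP section 3.0 presents the SAP as an elaboration of the protocol's methods, so a narrower definition should be announced and justified. The SAP does this elsewhere: section 11.3.2 says openly that laboratory grading moves from RCTC to CTCAE, and why. Section 11.2.1 has no such note. (Section 14.1, on changes from the protocol, shows no text in the copy supplied. I draw nothing from that.)

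The SAP also treats worsening differently across safety domains. Potentially important laboratory and vital-sign findings count when the post-baseline value is more extreme than baseline, so deterioration from an already abnormal start is seen. For AEs it is not.

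At stake is the completeness of the treatment-emergent tables: overview, system organ class and preferred term, maximum severity, relationship, and rate per 100 patient-years. A non-serious AE that begins in screening at Grade 1 and reaches Grade 3 on risankizumab could be absent from all of them. The omission applies equally to every arm. If the drug aggravates existing events, however, the loss falls mainly on the risankizumab arms and weakens the contrast with placebo.

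**Working it through.** No figure in the plan needs reproducing, because the point turns on a definition.

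**Step 1. Do the windows differ?** The protocol's residual effect period is 15 weeks and the SAP uses 105 days. 15 × 7 = 105, so they agree. Of the protocol's two routes, only the one for worsening is missing.

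**Step 2. Can such AEs exist?** Collection starts at consent, and the screening visit falls between Day -42 and Day -14. Every patient therefore has at least two weeks in which an AE can start before the first dose.

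**Step 3. Apply both rules to illustrative events**, reading the SAP definition period by period.

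| Event | Protocol 7.3.4 | SAP, Part A | SAP, Part B |
|---|---|---|---|
| A. Risankizumab arm, onset Day -10, worsens Day 5, one record | Treatment-emergent | No | No |
| B. As A, but the worsening is entered as a new AE with onset Day 5 | Treatment-emergent | Yes | No |
| C. Onset on Day 1 before dosing, worsens after dosing, one record | Treatment-emergent | No | No |
| D. Placebo patient, onset Day 60, worsens Day 120 after first risankizumab on Day 113, one record | Treatment-emergent (by onset) | Yes, under placebo | No |

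A and C are the conflict. B shows that the conflict disappears if sites open a new record. D is treatment-emergent under both documents: its onset is after first drug intake, so the protocol's worsening clause does not come into play.

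**Step 4. Does anything else in the SAP restore the clause?** No. The pre-treatment listing and the listing in 11.2.2 cover serious events and deaths only. A non-serious event of type A or C appears in no planned AE summary table.

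**Step 5. Who could be affected?** All 168 planned patients have a first drug intake, so all are exposed to A and C. D concerns the placebo patients who switch: 168 split 2:2:1:1 gives 56, 56, 28 and 28, so 28 + 28 = 56. The documents give no rate of AEs open at first dose and no rate of worsening, so no count follows.

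**The case against.** The strongest reply is that the gap is mostly closed by other means.

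- *Data capture.* Protocol 5.3.6.2 has worsening of pre-existing conditions recorded as an (S)AE, and Protocol 8.3.1 makes an onset date mandatory. A separate record would have a post-dose onset and meet the SAP definition. Protocol 6.2.1 also sends many screening findings to the baseline-condition page. This stands in part. It does not clearly cover an AE that began after consent, and nothing says that a worsened AE gets a new record.
- *Serious events.* SAP 11.2.2 still lists them, and laboratory and vital-sign deterioration has its own tables. This stands: the residual gap is mainly non-serious clinical AEs in summary tables.
- *Derivation.* The clause can be programmed only if the eCRF holds a new record or a dated change in severity. The documents do not say which. This stands and shapes the fix.

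Two stronger readings are tempting. A reader might infer that worsening after the first *risankizumab* dose is lost in breach of the protocol, including after the Week 16 switch. The documents do not support this. The clause is tied to first drug intake, which for placebo patients is the Day 1 placebo dose, and an AE that begins on placebo is already counted in Part A.

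A reader might also attach a number. If 5% to 10% of 168 patients had an open AE and 10% to 20% of those worsened, the result would be 168 × 0.05 × 0.10 = 0.8 to 168 × 0.10 × 0.20 = 3.4 patients. Both rates are guesses with no anchor in the documents, so I do not use the result.

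**Conclusion.** The point holds in limited form. SAP 11.2.1 conflicts with a stated protocol rule, does not say so, and no other SAP section repairs it. The consequence is confined to AEs that start between consent and first dose and worsen on drug under their original onset date. These drop out of every treatment-emergent summary table, though not out of the listings if serious.

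The size cannot be computed and is probably small, because an event must be post-consent, still open at first dose, worsening, and kept on one record. Efficacy, power and type I error are untouched. The conclusion assumes that at least some sites keep a worsened AE on its original record. If the eCRF rules always force a new record, the difference is one of wording only.

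The Week 16 switch is a separate and weaker matter. The SAP's period-by-period onset rule shows an AE that began on placebo only under placebo in Part A, even if it worsens on risankizumab. That is a presentational weakness, not a departure from the protocol.

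**What to change.** Add to the definition in SAP 11.2.1: *or an event with onset before the first dose of study drug that increases in severity after that dose, within the same 105-day/next-period window*. State that worsening is identified from a new AE record or from a dated severity change in the eCRF, whichever the data capture provides. If the sponsor prefers the onset-only rule, the SAP should name it as a departure from Protocol 7.3.4 and justify it.

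As an option beyond the protocol, apply the same rule relative to the first risankizumab dose for ex-placebo patients in Part B and for ALL_RZB. This would match SAP section 6.0, which already resets the safety baseline to that dose for both analyses.

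The cost is one clause, one sentence on data capture and a small derivation. The derivation is feasible only if severity changes are dated or re-recorded, so that should be checked first. The change is best made before the Week 28 unblinding.

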6.2.3.2 Trial completion

Patients who finish the randomised treatment period will return to the clinic for Follow-Up 1 Visit (FU1) and Follow-Up 2 Visit (FU2). Completion is defined as a patient having reached the FU2 visit within the specified window per the Flow Chart. Patients who complete the randomised treatment period without early treatment discontinuation will have the option to participate in the extension trial.

After FU1 Visit, the Flow Chart visit schedule is dependent on extension participation:

- Patient who will not participate in the extension trial will return to the clinic for FU2/EOO Visit and FU3/EOO Visit. Trial termination will be completed at FU3/EOO. The decision not to enter the extension trial will be registered in IRT at FU2/EOO Visit.
- Patients who participate in the extension trial will complete FU2/EOO as the final 1311.38 study visit. Trial termination will be completed at FU2/EOO and registered in IRT.

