3.0 Introduction

This Statistical Analysis Plan (SAP) describes the statistical analysis to be completed by the AbbVie Clinical Statistics Department for risankizumab study Protocol M16-004 (BI Study 1311.38) dated 05 September 2016 and the protocol amendment dated 07 June 2017.

This SAP will provide details to further elaborate statistical methods as outlined in the Protocol of Study 1311.38.

Analyses will be performed using SAS® version 9.4 (SAS Institute, Inc., Cary, NC 27513) or higher using the UNIX operating system.

SAP will not be updated in case of future administrative or minor amendments to the protocol unless the changes have any impact on the analysis of the study data.

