Table 4.
Visit Windows for Analysis of ECG in Part A (Safety Population)

Window Label	Target Day	Interval
Baseline	1	≤ 1
Week 4	29	[2, 71]
Week 16	113	[72, 155*]

Rx Day calculated relative to first dose date of study drug.

* The minimum of upper bound, the first dose date in Part B, and the last dose + 105 days.

Table 5. Visit Windows for Analysis of sPGA, PSS, DLQI, HAQ-DI, Pain VAS, Investigator's Global Assessment VAS, Patient's Global Assessment VAS, CRP as an ACR 20 Component, SJC, and TJC in Part A (ITT Population)

Window Label	Target Day	Interval
Baseline	1	≤ 1
Week 16	113	[2, 225*]

Rx Day calculated relative to first dose date of study drug. For subjects randomized but not dosed, Rx Day calculated relative to Randomization.

* The minimum of upper bound and the day of the first dose date in Part B.

Table 6. Visit Windows for Analysis of PASI, Vital Signs, and Local Tolerability in Part B (ITT/Safety Population)

Window Label	Target Day	Interval
Entry of Part B	1	$\leq 1^a$
Week 22	43	[2, 64]
Week 28	85	[65, 106]
Week 34	127	[107, 148]
Week 40	169	[149, 190]
Week 46	211	[191, 232]
Week 52	253	[233, 267]
Week 56	281	[268, 295 ^b]

Rx Day calculated relative to the first dose date on or after Week 16 for PBO/RZB_75 and PBO/RZB_150 arms, and relative to the date of Week 16 visit for RZB_75/RZB_75 and RZB_150/RZB_150 arms. PASI only evaluated from Week 22 to 52. Local tolerability only evaluated from Week 22 to 40.

a. If time is collected for vital sign, restrict to records prior to the first dose of study drug in Part B.

b. The minimum of upper bound and 105 days after the last dose.

Subjects who enter the Open Label Extension Study 1311.31 will not have Week 56 evaluations.

Table 7. Visit Windows for Analysis of sPGA, PSS, DLQI, HAQ-DI, Pain VAS, Investigator's Global Assessment VAS, Patient's Global Assessment VAS, SJC, TJC, Laboratory Tests, and ECG in Part B (ITT/Safety Population)

Window Label	Target Day	Interval
Entry of Part B	1	≤ 1
Week 28	85	[2, 127]
Week 40	169	[128, 211]
Week 52	253	[212, 294 ^a]

Rx Day calculated relative to the first dose date on or after Week 16 for PBO/RZB_75 and PBO/RZB_150 arms, and relative to the date of Week 16 visit for RZB_75/RZB_75 and RZB_150/RZB_150 arms.

a. The minimum of upper bound and 105 days after the last dose.

Table 8. Visit Windows for Summary of Study Drug Injections in Part A

Window Label	Target Day	Time Window
Week 0	1	≤ 1
Week 4	29	[2, 57 ^a]

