9.0 Study Drug Exposure and Compliance

Summary of study drug treatment duration and compliance will be provided for each treatment arm in each treatment period under the ITT Population.

Study drug treatment duration (days) will be summarized using the sample size, mean, standard deviation, minimum, median and maximum. In addition cumulative exposure of RZB (including total patient years) will also be summarized in the ALL_RZB Population. Study drug treatment duration will be summarized as follows:

Study Drug Exposure (in Days) in Each Period:

Part A:

- For subjects who did not continue into Part B:
 - Date of last injection in Part A – Date of first injection in Part A + 84 days.
- For subjects who continued into Part B:
Minimum of
 - Date of first injection in Part B – Date of first injection in Part A
 - Date of last injection in Part A – Date of first injection in Part A + 84 days.

Part B:

Date of last injection in Part B – Date of first injection in Part B + 84 days.

ALL_RZB:

For study drug exposure during the administration of risankizumab in the ALL_RZB Population:

- Date of last injection of risankizumab – Date of first injection of risankizumab + 84 days.

A data cutoff date (December 15, 2017) will be applied during the interim analysis, and the duration of study drug exposure will be defined up to this cutoff date.

Compliance

There will be a summary of the number of subjects receiving study drug and dose at each study drug administration visit. This will be repeated on the cumulative number of doses.

When computing compliance at each study drug administration visit, the denominator will include all subjects in each analysis population who have not prematurely discontinued the study drug prior to the scheduled study drug injection. Subjects who have prematurely discontinued the study drug but have not prematurely discontinued the study are not used in the denominator.

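### The patient-year denominator for entire-study AE rates has no end at trial exit, so about 21 credited days per extension patient are not actively observed in this trial

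*SAP*

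**What the plan says.** SAP 11.2.1 (adverse events per 100 patient-years) sets the scope: "AEs occurring during the entire study will be presented by event rate per 100 patient years". The rates cover any TEAE, serious events and areas of safety interest. Each subject's contribution to the denominator is the last dose date minus "date of first dose + 105 days (5 half-lives", summed over all subjects and divided by 365.25. No end at trial exit or extension entry is stated.

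The TEAE definition in the same section also runs to 105 days after the last dose, with one truncation: "or prior to the first dose in the subsequent period for subjects who entered in to the subsequent period". For the interim analysis there is a further limit: "The data cutoff date (December 15, 2017) will be applied to TEAEs during the interim analysis". SAP 9.0 cuts exposure at the same date, and its Part A exposure is a minimum of two terms, one of which is "Date of first injection in Part B – Date of first injection in Part A".

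On follow-up, Protocol 6.2.3.2 says: "Patients who participate in the extension trial will complete FU2/EOO as the final 1311.38 study visit". The note to SAP Table 6 agrees: "Subjects who enter the Open Label Extension Study 1311.31 will not have Week 56 evaluations". Protocol 3.1 follows patients outside the extension for adverse events until 16 weeks after their last dose. Under Protocol 5.3.6.2, all adverse events are collected until the individual patient's end of trial. After that there is no active monitoring, and the investigator reports only relevant SAEs and AESIs that come to attention.

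**The concern.** A rate per patient-year is interpretable only if the time in the denominator is time during which events would have been captured. For rollover patients the formula credits 105 days after the last dose, whereas this trial actively observes them for about 84. The extra days can add almost nothing to the any-TEAE numerator unless events from the extension trial are brought in, and neither document says that they are. The SAP's stated scope is "risankizumab study Protocol M16-004 (BI Study 1311.38" and the rate refers to the entire study, which points towards leaving them out.

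Followed as written, the rule lowers the rate. Protocol 7.7 sizes the trial largely around long-term safety data, so the entire-study rates are among the outputs readers will look at.

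**Working it through.** **Inputs**
- Nominal days (Protocol Flow Chart): first dose Day 1, EOT (Week 40) Day 281, FU2 (Week 52) Day 365, FU3 (Week 56) Day 393.
- Last dose at Week 40 (Protocol Table 4.1.4: 1).
- Residual effect period of 15 weeks (Protocol 5.3.6.2 and 7.3.4).
- 56 patients per risankizumab arm (Protocol 7.7). SAP Table 1 lists only the two risankizumab arms for the entire study.
- Rollover share *f*: not given, so 25% to 100% is shown.

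**The plan's own figure.** 15 × 7 = 105 days, which matches SAP 11.2.1.

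**Observed time after the last dose**
- Extension patients: 365 − 281 = 84 days, so 105 − 84 = 21 credited days lie after trial exit.
- Other patients: 393 − 281 = 112 days (16 weeks), which covers the 105 days.

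**Per patient, with the SAP's day count**
- Credited: (281 − 1) + 105 = 385 days.
- Observed, extension patient: 365 − 1 = 364 days.

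**Effect on the rate.** With a constant event rate, full completion and no extension-trial events counted, the mean observed time is 385 − 21*f* days against 385 credited. The relative understatement is 21*f*/385. Credited patient-years per arm are 56 × 385/365.25 = 59.0.

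| Rollover share | Observed patient-years, 56 × (385 − 21*f*)/365.25 | Excess patient-years | Rate understated by |
|---|---|---|---|
| 25% | 58.2 | 0.8 | 1.4% |
| 50% | 57.4 | 1.6 | 2.7% |
| 75% | 56.6 | 2.4 | 4.1% |
| 100% | 55.8 | 3.2 | 5.5% |

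**Scale.** The 100% figure (5.45%) equals one Poisson standard error of the rate when 1/√N = 21/385, that is N = (385/21)² = 336 events in an arm, or 336/59.03 × 100 = 569 per 100 patient-years. With fewer events, even the largest figure in the table is below one standard error.

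**The case against.** The strongest reply is that numerator and denominator use the same 105 days. That period is the protocol's residual effect period, and Protocol 7.3.4 assigns all events within it to treatment. Rollover patients continue in Study 1311.31, and if its events up to last dose + 105 days feed this rate, the shortfall shrinks or disappears. What stands is that the result is conditional. It does not remove the point, because the plan never says that extension events count, nor how events after the first extension dose would be attributed.

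It can also be said that the truncations elsewhere in the SAP are boundaries between periods of this trial or apply only at the interim, and that the Part B and ALL_RZB exposure formulas in SAP 9.0 have no cap at exit either. This is fair: those rules show that the SAP uses truncation, but they do not make the missing cap an internal contradiction.

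Three stronger readings are tempting but not supported:
- *Larger figures from visit windows.* Combining a late EOT with an early final visit widens the gap, but nothing suggests that whole groups would fall at opposite window extremes. For patients outside the extension, Protocol 3.1 sets follow-up at 16 weeks, which covers the 105 days.
- *A further loss from patients who stop drug early but stay in the trial.* Protocol 5.3.6.2 can be read as limiting their reporting to related SAEs and AESIs. However, the Flow Chart marks adverse events at every visit, and its note 11 asks these patients to complete the remaining visits. This is a separate protocol point, and those passages should be reconciled. These patients cannot enter the extension (Protocol 6.2.3.1), so they are not part of the rollover gap.
- *A biased comparison with placebo.* SAP Table 1 has no placebo group for the entire study.

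**Conclusion.** The point holds as a minor correction. The stated rule puts about 21 days per rollover completer into the denominator that this trial does not actively observe. At the final analysis the any-TEAE rate per risankizumab arm is understated by 1.4% to 5.5% at 25% to 100% rollover. This rests on four assumptions: extension-trial events are not counted, all patients complete treatment, visits fall on nominal days, and the event rate is constant. Protocol 7.7 shows that rollover is planned, since it expects patients to reach one year of exposure here or in the extension, but neither document gives the share.

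The consequence is limited. The rate is descriptive, and no hypothesis test or placebo contrast depends on it. SAE rates are affected less, because relevant SAEs can still be reported after trial exit. The comparison between doses changes little if rollover is similar in the two arms. The interim analysis has its own cutoff, so these figures concern the final analysis.

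**What to change.** Define each subject's time at risk as running from first dose to the earliest of:
- last dose + 105 days;
- end of observation in 1311.38 (FU2 for rollover patients; last contact or death otherwise);
- any data cutoff.

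Keep the current day count, and include in the rate only TEAEs with onset in that interval. SAEs and AESIs reported passively after that date stay in the TEAE counts and listings, with a footnote explaining why the two counts differ.

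The cost is one or two lines of SAP text and a small change to the derivation. Any-TEAE rates would rise slightly. A sparse SAE or safety-interest rate could fall instead, if a late passive report leaves its numerator; the footnote should make this visible.

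Alternatively, state that extension-trial events up to last dose + 105 days are counted, say how events after the first extension dose are attributed, and keep the 105 days for rollover patients. This avoids the two counts for those patients but requires extension-trial data.
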